6.5.4 Guidelines for the management of specific adverse events

Specific adverse events described in sections below may classify as adverse events of special interest (AESIs), depending on grading according to National Cancer Institute- Common Terminology Criteria for Adverse Event (NCI-CTCAE) V5.0 (see Section 8.3.8 of the master protocol). In case a specific adverse event meets the AESI definition it must be documented in the e-CRF.

6.5.4.1 Infusion-related reactions (IRR)

Participants should routinely receive premedication as detailed in Section 6.1.2.1 of the master protocol prior to SAR444245 administration, to prevent or reduce the incidence or severity of IRRs.

An infusion-related reaction in this study is defined as any signs or symptoms which develop during the infusion or up to 24 hours after the completion of the infusion. The term IRR indicates only a specific temporal relationship with the infusion and does not specify a particular mechanism underlying the signs or symptoms.

Pembrolizumab may cause severe or life-threatening infusion-reactions including severe hypersensitivity or anaphylaxis. Signs and symptoms usually develop during or shortly after drug infusion and generally resolve completely within 24 hours of completion of infusion. Dose modification and toxicity management guidelines on pembrolizumab-associated infusion reaction are provided in [Table 5](#).

After an infusion-related reaction due to pembrolizumab infusion (Grade 3 or Grade 4), the SAR444245 infusion will be delayed and can be administered after resolution of symptoms. The Investigator should discuss with the Sponsor's Medical Monitor if the SAR444245 infusion needs to be delayed more than 1 day.

Guidelines for the management of SAR444245 IRR events are provided in [Table 6](#). Participants who develop Grade 2 IRR should have the next SAR444245 infusion given at half the infusion rate. For instructions on premedication at subsequent dosing, please see Section 6.1.2.1 of the master protocol.

Table 5 - Pembrolizumab infusion-related reaction dose modification and treatment guidelines

NCI CTCAE Grade	Treatment	Premedication at subsequent dosing
Grade 1 Mild transient reaction; infusion interruption not indicated; intervention not indicated	
 • Increase monitoring of vital signs as medically indicated until the participant is deemed medically stable in the opinion of the investigator. 	None
Grade 2 Requires therapy or infusion interruption but responds promptly to symptomatic treatment (eg, antihistamines, NSAIDs, narcotics, IV fluids); prophylactic medications indicated for ≤24 hrs.	
 • Stop Infusion. • Additional appropriate medical therapy may include but is not limited to: 
 - IV fluids, - Antihistamines, - NSAIDs, - Acetaminophen, - Narcotics. • Increase monitoring of vital signs as medically indicated until the participant is deemed medically stable in the opinion of the investigator. • If symptoms resolve within 1 hour of stopping drug infusion, the infusion may be restarted at 50% of the original infusion rate (eg, from 100 mL/hr. to 50 mL/hr.). Otherwise, dosing will be held until symptoms resolve and the participant should be premedicated for the next scheduled dose. 	
Participant may be premedicated 1.5 h (\pm30 minutes) prior to infusion of pembrolizumab with: Diphenhydramine 50 mg po (or equivalent dose of antihistamine). Acetaminophen 500-1000 mg po (or equivalent dose of analgesic).

Participants who develop Grade 2 toxicity despite adequate premedication should be permanently discontinued from further study drug treatment		
Grades 3 or 4 Grade 3: Prolonged (ie, not rapidly responsive to symptomatic medication and/or brief interruption of infusion); recurrence of symptoms following initial improvement; hospitalization indicated for other clinical sequelae (eg, renal impairment, pulmonary infiltrates)	
 • Stop Infusion. • Additional appropriate medical therapy may include but is not limited to: 
 - Epinephrine*, - IV fluids, - Antihistamines, - NSAIDs, - Acetaminophen, - Narcotics, - Oxygen, - Pressors, - Corticosteroids. 	No subsequent dosing
Grade 4: Life-threatening; pressor or ventilator support indicated	
 • Increase monitoring of vital signs as medically indicated until the participant is deemed medically stable in the opinion of the investigator. • Hospitalization may be indicated. 	
*In cases of anaphylaxis, epinephrine should be used immediately. Participant is permanently discontinued from further study drug treatment.		

Appropriate resuscitation equipment should be available at the bedside and a physician readily available during the period of drug administration. For further information, please refer to the Common Terminology Criteria for Adverse Events v5.0 (CTCAE) at <http://ctep.cancer.gov>.

Table 6 - SAR444245 infusion-related reaction dose modification and treatment guidelines

NCI CTCAE Grade	Treatment
Grade 1 Mild transient reaction; infusion interruption not indicated; intervention not indicated	If IRR happens during infusion, continuation of SAR444245 ^a infusion is per Investigator's judgment following close direct monitoring of the participant's clinical status. SAR444245 infusion may be interrupted at any time if deemed necessary. If interrupted, IRR will be classified as Grade 2 as per NCI-CTCAE definition. If IRR happens after completion of infusion, increase monitoring of vital signs as medically indicated until the participant is deemed medically stable in the opinion of the investigator.
Grade 2 Requires therapy or infusion interruption but responds promptly to symptomatic treatment (eg, antihistamines, NSAIDs, narcotics, IV fluids); prophylactic medications indicated for ≤24 hrs.	SAR444245 infusion should be interrupted if applicable. If symptoms resolve within 1 hour of interrupting drug infusion, the infusion may be restarted at 50% of the original infusion rate. Otherwise, dosing will be held until symptoms resolve and the participant should be premedicated for the next scheduled dose according to Section 6.1.2.1 of the master protocol. The next infusion should be given at half the infusion rate. During or after completion of infusion, additional appropriate medical therapy may include but not limited to IV fluids, antihistamines, NSAIDs, acetaminophen, narcotics. Increase monitoring of vital signs will be as medically indicated until the participant recovers.
Grade 3 Prolonged (ie, not rapidly responsive to symptomatic medication and/or brief interruption of infusion); recurrence of symptoms following initial improvement; hospitalization indicated for other clinical sequelae	SAR444245 infusion should be interrupted if applicable. If IRR is clearly attributable to SAR444245, SAR444245 should be permanently discontinued. The participant can continue treatment with the other anti-cancer therapy in combination During or after completion of infusion, additional appropriate medical therapy may include but is not limited to epinephrine ^b , IV fluids, antihistamines, NSAIDs, acetaminophen, narcotics, oxygen, vasopressors, corticosteroids. Increase monitoring of vital signs as medically indicated until the participant recovers.
Grade 4 Life-threatening; pressor or ventilator support indicated	SAR444245 infusion should be interrupted if applicable. If IRR is clearly attributable to SAR444245, SAR444245 should be permanently discontinued. The participant can continue treatment with the other anti-cancer therapy in combination During or after completion of infusion, additional appropriate medical therapy may include but is not limited to epinephrine ^b , IV fluids, antihistamines, NSAIDs, acetaminophen, narcotics, oxygen, vasopressors, corticosteroids. Increase monitoring of vital signs as medically indicated until the participant recovers.

a Information for preparation and storage of SAR444245 are provided in the pharmacy manual.

b In cases of anaphylaxis, epinephrine should be used immediately

Abbreviations: CTCAE = Common terminology criteria for adverse events; IRR = Infusion-related reaction; NCI = National Cancer Institute; NSAIDs: nonsteroidal anti-inflammatory drugs.

Participants who experience cetuximab-related infusion reactions should have cetuximab reduced according to [Table 7](#) and continue to receive antihistamine premedication prior to administration. Once the cetuximab infusion rate has been decreased due to an allergic/hypersensitivity reaction, it should remain decreased for all subsequent infusions. If the participant experiences a second infusion reaction at the decreased rate, cetuximab should be permanently discontinued. If any Grade 3-4 infusion reaction occurs, cetuximab treatment should be discontinued immediately.

Severe infusion-related reactions, including anaphylactic reactions, may commonly occur, in some cases with fatal outcome. Occurrence of a severe infusion-related reaction requires immediate and permanent discontinuation of cetuximab therapy and may necessitate emergency treatment. Some of these reactions may be anaphylactic or anaphylactoid in nature or represent a cytokine release syndrome (CRS). Symptoms may occur during the first infusion and for up to several hours afterwards or with subsequent infusions.

Table 7 - Cetuximab infusion-related reaction dose modification and treatment guidelines

NCI CTCAE Grade	Dose modification
Grade 1 Mild reaction; infusion interruption not indicated; intervention not indicated	Decrease the cetuximab infusion rate by 50% and monitor closely for any worsening.
Grade 2 Requires therapy or infusion interruption but responds promptly to symptomatic treatment (eg, antihistamines, NSAIDs, narcotics, IV fluids); prophylactic medications indicated for ≤24 hrs	Stop cetuximab infusion and administer bronchodilators, oxygen, etc. as medically indicated. Resume infusion at 50% of previous rate once allergic/hypersensitivity reaction has resolved or decreased to Grade 1 in severity and monitor closely for any worsening.
Grades 3 or 4 Grade 3: Prolonged (ie, not rapidly responsive to symptomatic medication and/or brief interruption of infusion); recurrence of symptoms following initial improvement; hospitalization indicated for other clinical sequelae (eg, renal impairment, pulmonary infiltrates) Grade 4: Life-threatening; pressor or ventilator support indicated	Stop the cetuximab infusion immediately, administer epinephrine, bronchodilators, antihistamines, glucocorticoids, intravenous fluids, vasopressor agents, oxygen, etc., as medically indicated. Cetuximab should permanently discontinued. The participant can continue treatment with SAR444245.

Abbreviations: CTCAE = Common terminology criteria for adverse events; IRR = Infusion related reaction; NCI = National Cancer Institute.

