Infusion reactions	
Pembrolizumab
 
Common, but infusion-related reactions in labeling include drug hypersensitivity, anaphylactic reaction, anaphylactoid reaction, hypersensitivity and cytokine release syndrome.
 
Cetuximab
 
Severe infusion-related reactions, including anaphylactic reactions, may commonly occur, in some cases with fatal outcome. Symptoms may occur during the first infusion and for up to several hours afterwards or with subsequent infusions. Symptoms may include bronchospasm, urticaria, increase or decrease in blood pressure, loss of consciousness or shock. In rare cases, angina pectoris, myocardial infarction or cardiac arrest have been observed.
 
Anaphylactic reactions may occur as early as within a few minutes of the first infusion and can occur despite the use of premedication.
 
The risk for anaphylactic reactions is much increased in patients with a history of allergy to red meat or tick bites or positive results of tests for IgE antibodies against cetuximab (α-1-3-galactose). In these patients cetuximab should be administered only after a careful assessment of benefit/risk, including alternative treatments, and only under close supervision of well-trained personnel with resuscitation equipment ready.
 
A cytokine release syndrome (CRS) typically occurs within one hour after infusion and is less commonly associated with bronchospasm and urticaria. CRS is normally most severe in relation to the first infusion. Mild or moderate infusion-related reactions are very common comprising symptoms such as fever, chills, dizziness, or dyspnea that occur in a close temporal relationship mainly to the first cetuximab infusion
	
Pembrolizumab
 
Dose modification and treatment guidelines for pembrolizumab infusion associated reactions are provided in Table 5.
 
Cetuximab
 
Occurrence of a severe infusion-related reaction requires immediate and permanent discontinuation of cetuximab therapy and may necessitate emergency treatment.
 
It is recommended to warn patients of the possibility of such a late onset and instruct them to contact their physician if symptoms or signs of an infusion-related reaction occur.
 
The first dose should be administered slowly and the speed must not exceed 5 mg/min whilst all vital signs are closely monitored for at least two hours. If during the first infusion, an infusion-related reaction occurs within the first 15 minutes, the infusion should be stopped. A careful benefit/risk assessment should be undertaken including consideration whether the patient may have performed IgE antibodies before a subsequent infusion is given.
 
Premedicate with a histamine-1 (H1) receptor antagonist prior to cetuximab administration. Monitor patients for at least 1 hour following each cetuximab infusion, in a setting with resuscitation equipment and other agents necessary to treat anaphylaxis. Initiate SAR444245 infusion only when no infusion reaction has occurred after 1-2 hours of observation. In patients requiring treatment for infusion reactions, use recommended per the country-approved product labeling (eg, USPI, SmPC) for cetuximab.
 
If an infusion-related reaction develops later during the infusion or at a subsequent infusion further management will depend on its severity:

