
Potential risk of clinical significance	Summary of data/rationale for risk	Mitigation strategy
	
a) Grade 1: continue slow infusion under close supervision
 
b) Grade 2: continue slow infusion and immediately administer treatment for symptoms
 
c) Grade 3 and 4: stop infusion immediately, treat symptoms vigorously and contraindicate further use of cetuximab
	
Immunogenicity (Anti-drug antibodies)	
Cetuximab
 
The development of human anti-chimeric antibodies (HACA) is a class effect of monoclonal chimeric antibodies. Current data on the development of HACAs is limited. Overall, measurable HACA titers were noted in 3.4% of the patients studied, with incidences ranging from 0% to 9.6% in the target indication studies. No conclusive data on the neutralizing effect of HACAs on cetuximab is available to date. The appearance of HACA did not correlate with the occurrence of hypersensitivity reactions or any other undesirable effect to cetuximab.
	
Hypersensitivity, including anaphylaxis	
Pembrolizumab
 
Not specifically reported but included among infusion-related reactions in label.
 
Cetuximab
 
Please see above within Infusion reactions
	
Exclusion of participants with known hypersensitivity to any components of pembrolizumab.
 
Also, see specific instructions for cetuximab.

Infections	
Pembrolizumab
 
Common: pneumonia.
 
Cetuximab
 
Patients who receive cetuximab in combination with platinum-based chemotherapy are at an increased risk for the occurrence of severe neutropenia, which may lead to subsequent infectious complications such as febrile neutropenia, pneumonia or sepsis. Careful monitoring is recommended in such patients, in particular in those who experience skin
	See routine mitigation in the master protocol.

Potential risk of clinical significance	Summary of data/rationale for risk	Mitigation strategy
	
lesions, mucositis or diarrhea that may facilitate the occurrence of infections.
 
Further, the risk for secondary infections (mainly bacterial) of adverse skin reactions is increased and cases of staphylococcal scalded skin syndrome, necrotizing fasciitis and sepsis, in some cases with fatal outcome, have been reported
	

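### Substudy 04, Cohort D2: Section 6.5.4.1 with Table 7 and Appendix 11 Table 15 conflict on cetuximab after a repeat Grade 1-2 infusion reaction, and on a Grade 1 reaction in the first 15 minutes of the first infusion

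*Protocol*

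**What the plan says.** All of this is current text of substudy 04.

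**Section 6.5.4.1 and Table 7.** Once the cetuximab rate has been lowered for a reaction, it stays lowered at every later infusion. Then: "If the participant experiences a second infusion reaction at the decreased rate, cetuximab should be permanently discontinued". No grade is attached; Grade 3-4 reactions have their own sentence and lead to discontinuation at once. For Grade 1, Table 7 says: "Decrease the cetuximab infusion rate by 50% and monitor closely for any worsening". It makes no exception for timing. The cetuximab column of Table 8 (CRS, Section 6.5.4.3) gives the same Grade 1 instruction.

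**Appendix 11, Table 15, infusion reactions, mitigation column.** For an early reaction: "If during the first infusion, an infusion-related reaction occurs within the first 15 minutes, the infusion should be stopped". It goes on: "A careful benefit/risk assessment should be undertaken including consideration whether the patient may have performed IgE antibodies before a subsequent infusion is given". For any other reaction: "If an infusion-related reaction develops later during the infusion or at a subsequent infusion further management will depend on its severity". The severity list is:
- "Grade 1: continue slow infusion under close supervision"
- "Grade 2: continue slow infusion and immediately administer treatment for symptoms"
- "Grade 3 and 4: stop infusion immediately, treat symptoms vigorously and contraindicate further use of cetuximab"

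**Pointers between the two.** Section 6.5.1 places cetuximab dose modification under the guidelines of Section 6.5, and Section 6.5.4.3 refers readers to Table 7 for cetuximab reactions. Neither says which text prevails when Table 15 differs.

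**The concern.** Table 15 gives directive, grade-by-grade bedside instructions in a mitigation column, so a site could reasonably act on it. For pembrolizumab the same row only points to Table 5; for cetuximab it sets out a second algorithm.

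The conflicts carry risk in opposite directions. A site following Table 15 after a repeat Grade 1-2 reaction may re-expose a participant whom Section 6.5.4.1 takes off cetuximab. A site following Table 7 for an early Grade 1 reaction would keep the drug running at half rate, when Table 15 would stop it pending an IgE assessment. The protocol itself marks that early window as dangerous: Table 15 says anaphylaxis can begin minutes into the first infusion despite premedication, and Section 2.3.1.2 puts roughly 90% of severe reactions at the first infusion.

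At stake are uniform safety management and cetuximab exposure in a few participants. No statistical operating characteristic changes.

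**Working it through.** **Comparison by situation**

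| Situation | Section 6.5.4.1 / Table 7 | Table 15 | Agree? |
|---|---|---|---|
| Second Grade 1 or 2 reaction, at the decreased rate | Discontinue permanently | Continue slowly (Grade 2: also treat) | No |
| Grade 1, first 15 minutes of first infusion | Halve the rate, keep running | Stop; benefit/risk (IgE) assessment before re-dosing | No |
| Grade 3-4 | Stop, no further cetuximab | Stop, no further cetuximab | Yes |

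Table 15 does not name a repeat reaction. However, its severity rule covers a reaction at a subsequent infusion and contains no exception for recurrence. Because Section 6.5.4.1 makes the lowered rate permanent, a reaction at a later infusion after a rate cut necessarily occurs at the decreased rate. Both rules therefore apply to it.

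Infusion-speed limits and the handling of a single Grade 2 reaction are left out of this point.

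**Is there a tie-breaker?** Section 6.5.1 tells sites to take the most conservative adjustment, but for a participant with several toxicities that call for different actions. Here one reaction has two instructions, so the rule does not reach it.

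**Size of the first conflict**

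Inputs: any-grade reactions 8.4% and Grade 3-4 reactions 2.2% (Section 2.3.1.2); 40 participants in D2 (Section 9.2).

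- Grade 1-2 reactions: 8.4% − 2.2% = 6.2%.
- Expected participants with a first Grade 1-2 reaction: 40 × 0.062 = 2.48.
- Chance of at least one: 1 − (1 − 0.062)^40 = 1 − 0.938^40 = 92.3%.

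The document gives no recurrence rate. Let r be the assumed share of these participants who react again at the decreased rate. The expected number is 40 × 0.062 × r, and the chance of at least one is 1 − (1 − 0.062r)^40.

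| Assumed r | Expected participants | Chance of at least one |
|---|---|---|
| 10% | 0.25 | 22.0% |
| 25% | 0.62 | 46.5% |
| 50% | 1.24 | 71.6% |
| 100% (limit) | 2.48 | 92.3% |

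**Size of the second conflict.** The share of Grade 1 reactions that start in the first 15 minutes of the first infusion is not given. On the pooled rates, these cases are some unknown part of the 2.48.

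**The case against.** The strongest reply is that Section 6.5 is the operative text and Appendix 11 only background. Section 6.5.1 points to Section 6.5, Section 6.5.4.3 points to Table 7, and Appendix 11 introduces Table 15 as available information. A specific recurrence rule would normally override a general severity list, which can be read as managing only the infusion in progress. This largely answers the repeat reaction, and the point concedes that Section 6.5.4.1 is favoured there. It does not help with the early reaction: if Section 6.5 alone governs, the stricter stop rule and the IgE assessment disappear, because they stand only in Table 15.

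A second reply is that Table 7 does not forbid stopping, and that a reaction for which the infusion is interrupted becomes Grade 2 (Table 6 says so for SAR444245, citing CTCAE), which Table 7 also stops. But nothing in Table 7 prompts the stop. Its Grade 2 row also resumes at half rate after recovery, without the benefit/risk step.

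Three smaller points have force:
- A change to Table 8 adds little once Table 7 is amended, since Section 6.5.4.3 already refers cetuximab reactions there.
- The 8.4% and 2.2% are pooled rates. D2 may include participants already treated with cetuximab, Table 15 calls mild or moderate reactions very common, and Section 2.3.1.3 expects the combination may raise frequency and severity.
- The master protocol and pharmacy manual are not at hand, so the absence of a precedence clause is asserted only for the text seen.

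**Conclusion.** The concern holds. For a repeat Grade 1-2 reaction and for a Grade 1 reaction in the first 15 minutes of the first infusion, two parts of the same substudy protocol prescribe incompatible actions, and no visible clause resolves it. Treating Section 6.5 as governing settles the first case but drops the early-stop safeguard in the second, so this is more than an editorial slip.

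The reach is small: about 2.5 of 40 participants with a first Grade 1-2 reaction, and about 0.2 to 1.2 meeting the first conflict at an assumed recurrence of 10% to 50%. These figures assume that the pooled rates carry over to D2 and that participants are independent. The upper limit of 2.5 holds only on those pooled rates. The second conflict is not quantified. The discrepancy should be corrected for participant safety; confidence is medium.

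**What to change.** 1. State in Section 6.5.4.1 that this section and Table 7 govern cetuximab infusion reactions, and keep permanent discontinuation for a second reaction of any grade at the decreased rate.
2. Add the early-reaction rule to Table 7: for any reaction in the first 15 minutes of the first infusion, stop, and complete a benefit/risk assessment that considers IgE before any further infusion.
3. Make the Grade 1 cetuximab cell of Table 8 subject to the same exception.
4. Replace the grade-by-grade cetuximab text in Table 15 with a cross-reference to Section 6.5.4.1 and Table 7, as that row already does for pembrolizumab.

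The cost is a wording change in Section 6.5.4.1, Tables 7 and 8 and one row of Table 15. It adds no visits and no data collection.
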